## **Eligibility Criteria**

Inclusion Criteria:

- 1) diagnosis of ischemic or hemorrhagic stroke
- 2)  $\geq 6$  months and  $\leq 5$  years post-stroke
- 3)  $\geq 18$  years of age
- 4) ambulatory in the community with or without an assistive device (e.g. walker, cane)
- 5) self-reported sedentary behavior ( $\geq 6$  hours/day of sedentary behavior reported using the Sedentary Behavior Questionnaire)
- 6) reside within 50 miles of Pittsburgh

Exclusion Criteria:

- 1) severe aphasia (Boston Diagnostic Aphasia Examination score  $\leq 1$ )
- 2) currently receiving outpatient or home care rehabilitation services (physical therapy, occupational therapy, or speech therapy)
- 3) current active cancer treatment
- 4) medical history of neurodegenerative disorder (i.e. dementia, Parkinson's disease, multiple sclerosis, Lou Gehrig's disease (ALS), glioblastoma, myasthenia gravis)
- 5) current major depressive disorder, psychiatric condition, substance abuse (assessed via in-person participant interview after signed informed consent, using Patient Health Questionnaire-9, PRIME-MD/MINI)

## **Statistical Considerations**

**Primary Outcome Measures:**

1. Change in daily sedentary time accumulated in bouts greater than or equal to 30 minutes (Baseline to Week 11), ActivPAL
2. Change in daily number of sedentary breaks (Baseline to Week 11), ActivPAL

**Secondary Outcome Measures:**

1. Change in daily number of sedentary breaks (Baseline to Week 18), ActivPAL
2. Change in daily sedentary time accumulated in bouts greater than or equal to 30 minutes (Baseline to Week 18), ActivPAL
3. Change in Participation (Baseline to Week 11), Stroke Impact Scale-Participation Subscale
4. Change in Participation (Baseline to Week 18), Stroke Impact Scale-Participation Subscale

*PRELIMINARY DATA SCREENING:*

We will explore distributions of all descriptive and outcome variables to understand the variance and identify outliers in our data set. We will examine our data set to identify patterns of missing data and descriptive characteristics for whom data were missing.

**PRIMARY AND EXPLORATORY OUTCOMES**

This study employs a delayed baseline design to allow assessment of baseline stability. We will examine stability on primary and secondary outcomes between baseline 1 (week 1) and baseline 2 (week 6). We will then compute a single mean baseline score for each participant using baseline 1 (week 1) and baseline 2 (week 6).

We will then compute within-person change scores between baseline and post-intervention (week 11) and between baseline and follow-up (week 18). The group's mean change score and standard deviation will be reported.

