## **Study Design & Methods**

The study is a single-group quasi-experimental study that will estimate within-group effects of the ABLE intervention on sedentary behavior. All assessment at intervention procedures will be completed by trained research staff (research assistants, interventionists) with supervision provided by the principal investigator.

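### The secondary week-18 mean change covers only participants who still have a week-18 score, so response-related dropout after week 11 would bias it and nothing in the plan corrects for that

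*Combined protocol and SAP*

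**What the plan says.** Study Design & Methods describes the trial this way: "The study is a single-group quasi-experimental study that will estimate within-group effects of the ABLE intervention on sedentary behavior". There is no comparison arm.

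The primary outcomes run to week 11, for example "Change in daily number of sedentary breaks (Baseline to Week 11), ActivPAL". The week-18 versions are secondary, for example "Change in daily sedentary time accumulated in bouts greater than or equal to 30 minutes (Baseline to Week 18), ActivPAL".

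Primary and Exploratory Outcomes gives the whole estimation method in three steps. The first is to "compute a single mean baseline score for each participant using baseline 1 (week 1) and baseline 2 (week 6". The second is: "We will then compute within-person change scores between baseline and post-intervention (week 11) and between baseline and follow-up (week 18". The third is: "The group's mean change score and standard deviation will be reported".

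The only provision for missing data is under Preliminary Data Screening: "We will examine our data set to identify patterns of missing data and descriptive characteristics for whom data were missing". The plan names no repeated-measures model, imputation, common analysis set or sensitivity analysis. It also does not say how a participant with only one baseline recording is handled.

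**The concern.** A within-person change score exists only when both of its parts exist. The planned week-18 mean is therefore an available-case mean. The plan does not state this as a rule; it follows from the arithmetic. A participant who leaves between the two assessments has two baselines and a week-11 recording, yet contributes nothing to the week-18 estimate.

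Some loss is plausible. Each participant is asked for four 7-day, 24-hour recordings and up to 12 sessions, and the last assessment comes 8 weeks after the intervention ends. If those who gained less are the ones who leave, the remaining group looks better at week 18 than the full group would have. The Study Objectives ask for effects at both post-intervention and follow-up, so readers will set the two means side by side even though they may come from different people. With no control arm, such bias has no chance of cancelling between groups.

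**Working it through.** The plan states no sample size, SD, effect size, correlation or dropout rate, so there is no figure of its own to reproduce. Everything below rests on assumed inputs.

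**Assumed inputs (sedentary time in long bouts).** SD σ = 120 min/day at each of four assessments; correlation ρ = 0.7 between any two; true mean changes of −45 min/day at week 11 and −30 at week 18. Loss after week 11 depends on which half of the week-11 change distribution a participant falls in.

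**Step 1: spread of the change scores.** Let B be the mean of the two baselines.
- Var(B) = σ²(1+ρ)/2 = 14,400 × 0.85 = 12,240.
- Var(week-11 change) = σ² + Var(B) − 2ρσ² = 14,400 + 12,240 − 20,160 = 6,480, so the SD is 80.5.
- Cov(week-11 change, week-18 change) = ρσ² − 2ρσ² + Var(B) = 10,080 − 20,160 + 12,240 = 2,160.
- Slope of week-18 change on week-11 change = 2,160 / 6,480 = 1/3.

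**Step 2: shift among those who stay.** In a normal distribution each half lies 0.798 SD from the centre on average: 0.798 × 80.5 = 64.2 min/day.
- Loss 10% (better half) and 40% (worse half): the better half makes up 0.9/(0.9+0.6) = 0.60 of stayers. The shift in week-11 change is (0.60 − 0.40) × 64.2 = 12.8, and in week-18 change 12.8/3 = 4.3.
- Loss 5% and 15%: the better half makes up 0.95/(0.95+0.85) = 0.528. The shift is 0.056 × 64.2 = 3.6 at week 11 and 1.2 at week 18.
- Equal loss in both halves: shift 0.

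**Step 3: what the planned means would show.**

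| Loss (better / worse half) | Week 11, all | Week 11, stayers only | Week 18, as planned | True week 18 |
|---|---|---|---|---|
| 10% / 40% | −45 | −57.8 | −34.3 | −30 |
| 5% / 15% | −45 | −48.6 | −31.2 | −30 |
| equal | −45 | −45 | −30 | −30 |

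In the first row the fall-off after week 11 looks like about 11 min/day instead of 15. Changing ρ to 0.5 or 0.85 moves the first-row week-18 figure only to about −35.5 or −33.

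**Step 4: check by simulation.** At n = 2000 with 10%/40% loss, the week-18 mean as planned was −34.1, and a likelihood estimate using every recorded assessment gave −29.9.

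**Step 5: a different dropout model.** In SD units, let the true change be −0.50 at week 11 and −0.25 at week 18 (50% retained), with 20% loss following a logistic model in week-11 change (log-odds 0.5 to 1.0 per SD) and correlation 0.5 to 0.7 between the two change scores. The planned week-18 mean is then −0.30 to −0.37, so apparent retention is 60% to 74%. Loss unrelated to response gives 50%.

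**Step 6: small samples.** Root-mean-square error (min/day) of the week-18 estimate, 10%/40% loss:

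| Assumed n | Planned mean | Random-intercept model |
|---|---|---|
| 15 | 24.6 | 23.9 |
| 30 | 17.5 | 16.6 |

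An unstructured covariance gave 26.5 at n = 15, worse than the planned mean. The simulated data have equal correlations, which suits the random-intercept model, so its advantage here is a favourable case.

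**Step 7: where the model fails.** If the same 10%/40% loss depends on the week-18 response itself, the planned mean is about −43 and the likelihood estimate about −41, against a true −30.

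**The case against.** The strongest reply is about proportion. This is a single-group study meant to assess feasibility and estimate effects, with no planned test. At n = 30 a bias of 4 min/day is small beside a sampling SD of about 17, and it takes a fourfold difference in dropout to reach 4. People may leave for reasons that have nothing to do with response, or in a pattern that biases the other way. A mixed model also does nothing about regression to the mean or secular change. All of this stands, and it limits how much weight the point can carry. It does not remove the point: the estimates are the study's main product, the reported SD does not reveal bias, and the data needed for a better estimate will already have been collected.

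The second reply is that a simulation in which dropout depends on observed week-11 response favours the model by construction. That is also true, and Step 7 shows how little the model repairs otherwise. The fix therefore needs a sensitivity analysis.

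A reader might draw three stronger conclusions that the documents do not support:
- **That the primary week-11 results are biased.** The calculations place dropout only after week 11, and the week-11 mean in all participants stays at its true value.
- **That participants with one baseline recording are excluded.** The plan is silent on this. It defines an average of two baselines and gives no rule for when one is missing.
- **That the plan misestimates a maintenance effect it set out to measure.** No week-18 versus week-11 contrast is defined; the comparison is one that readers are likely to make for themselves.

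**Conclusion.** The point holds for the secondary week-18 results. The planned estimator drops anyone without a week-18 score, and the missing-data screening does not feed into it. If loss after week 11 is related to response, the week-18 mean is biased and is not comparable with the week-11 mean.

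The size cannot be determined from the documents. On the assumptions above it runs from zero, through about 1 min/day, to about 4 min/day (4.3/30, or 14% of the assumed week-18 effect). The direction, overstatement, rests on the further assumption that poorer responders are the ones who leave. This is a worthwhile improvement to the analysis plan and does not undermine the study.

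**What to change.** In Primary and Exploratory Outcomes, estimate the changes from one linear mixed model per outcome. Use the four assessments as a categorical time factor and a participant random intercept, which is a parsimonious covariance for what may be a small sample. Include everyone with at least one recording; this also settles how a participant with a single baseline is handled. Report week 11 minus the mean of the two baselines and week 18 minus that mean, with week 18 minus week 11 as a descriptive contrast.

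Keep the planned raw mean and SD of change as the descriptive table, with n at each time point. Show week-11 change separately for participants with and without week-18 data, so that readers can see whether loss was related to response.

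Add a simple sensitivity analysis, for example shifting the assumed week-18 change of those lost by a range of stated amounts. The model relies on missing-at-random and corrects little if people leave because of their unobserved week-18 status.

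The cost is SAP wording and one standard model per outcome, with no new data. With complete data the model returns the same point estimates as the planned means.
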